#### **4.3. Exclusion Criteria**

Subjects who meet *any* of the following exclusion criteria are not to be enrolled in this study:

- 1) Multi-organ transplant that includes heart or lung recipient (patients who have their liver transplant as part of a liver-kidney dual transplant are eligible to enroll)
- 2) Subjects with de novo or recurrent Hepatocellular Carcinoma (HCC) posttransplant

- 3) Current use of corticosteroids at any dose >5mg of prednisone/day (or equivalent dose of corticosteroid)
  - 4) Child-Pugh-Turcotte (CPT) Score >7 at Screening
  - 5) Recipient of ABO incompatible organ
  - 6) Histological evidence of unresolved rejection
  - 7) Infection with hepatitis B virus (HBV) or human immunodeficiency virus (HIV) at Screening
  - 8) Current, uncontrolled ascites, variceal hemorrhage, hepatic encephalopathy, hepatorenal syndrome, hepatopulmonary syndrome, or other signs of decompensated cirrhosis
  - 9) Serum creatinine >2.5x upper limit of normal (ULN) or stage 4 chronic kidney disease (CrCl <30ml/min)
  - 10) Screening ECG with clinically significant abnormalities
  - 11) Subjects with the following laboratory results at Screening are excluded unless enrollment is approved by the sponsor medical monitor
    - ALT, AST or alkaline phosphatase >10 x ULN
    - Direct bilirubin  $\geq 4$  x ULN
    - WBC <2,000/mm^3\*
    - ANC <1,000cells/mm^3\*
    - Platelets <50,000/mm^3\*
    - HbA1C >8.5%
    - Hemoglobin <9g/dL\*
- \*Use of GM-CSF, epoetin alfa or other therapeutic agents to increase cell counts for the purposes of meeting eligibility criteria is prohibited.
- 12) Use of GM-CSF, epoetin alfa or other therapeutic agents within 2 weeks of Screening
  - 13) History of other clinically relevant chronic liver disease (e.g., hemochromatosis, autoimmune hepatitis, Wilson's disease,  $\alpha$ -1-antitrypsin deficiency, alcoholic liver disease, non-alcoholic steatohepatitis, or toxin exposure)
  - 14) Recent (within 4 weeks of Screening) episode or infection requiring systemic antibiotics

- 15) Use or planned use of T-cell depleting/masking antibodies, systemic antineoplastic agents, cyclosporine >300mg/day, or use of any prohibited medications listed in Section 5.4 within 28 days of the Baseline/Day 1 visit
- 16) Prior exposure to any HCV NS5A inhibitor
- 17) History or current evidence of immunologic disorder, hemoglobinopathy, pulmonary or cardiac disease, porphyria, seizure disorder, poorly controlled diabetes, pancreatitis with elevated lipase, cancer, or a history of malignancy (with exception of certain resolved skin cancers or pre-transplant hepatocellular carcinoma; patients who received liver transplants for hepatocellular carcinoma must be 5 years post-transplant with no evidence of recurrence at Screening) that in the opinion of the investigator makes the subject unsuitable for the study
- 18) Treatment for HCV infection with experimental or approved regimens within 3 months of Baseline/Day 1.
- 19) Participation in a clinical study with an investigational drug, or biologic within 3 months prior to Baseline/Day 1
- 20) Clinically relevant alcohol or drug abuse within 12 months of Screening. A positive drug screen will exclude subjects unless it can be explained by prescribed medications; the diagnosis and prescription must be approved by the investigator
- 21) History or difficulty with blood collection and/or poor venous access for the purposes of phlebotomy
- 22) Known hypersensitivity to SOF (and the metabolites), and/or VEL

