### **5.4. Prior and Concomitant Medications**

Concomitant medications taken within 30 days of Screening, up to and including the date of the visit four weeks after discontinuation of study drug, need to be recorded in the source documents and eCRFs. All concomitant medications should be recorded in the source documents (including all blood products).

For subjects on a calcineurin inhibitor (e.g., tacrolimus, sirolimus, everolimus) for post-transplant immunosuppression, levels should be collected as per the standard schedule (or as clinically indicated) for dose management at the clinical site, and processed at the local laboratory. Management of the immunosuppression is not part of the clinical protocol, but levels and resulting dose adjustments will be recorded to assess whether the regimens required adjustment in correlation with resolution of the HCV infection.

The following medications are prohibited from 28 days prior to the Baseline/Day 1 visit through the end of study drug dosing:

- Use of corticosteroids at any dose > 5mg of prednisone/day (or equivalent dose of corticosteroid) for maintenance of immunosuppression is prohibited. However, use of steroids for the short term treatment of Acute Cellular Rejection (ACR) is up to the discretion of the Investigator.
- Investigational agents or devices for any indication

Concomitant use of certain medications or herbal/natural supplements (inducers of drug transporters i.e. P-gp) with study drug may result in pharmacokinetic interactions resulting in increases or decreases in exposure of study drug or these medication. The use of the following agents is prohibited from 28 days prior to Baseline/Day 1 through the end of study drug dosing. The use of amiodarone is prohibited from 60 days prior to Baseline/Day 1 through the end of study drug dosing.

Examples of representative medications which are prohibited or are to be used with caution are listed below:

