**Table 5-1. List of Disallowed/ Use with Caution Medications**

Drug Class	Agents Disallowed	Use with Caution
Acid Reducing Agents a		Proton Pump Inhibitors, H2-Receptor Antagonists, Antacids,
Anticonvulsants b	Phenobarbital, Phenytoin, Carbamazepine, Oxcarbazepine	
Antimycobacterials b	Rifabutin, Rifapentine, Rifampin	
Cardiac Medications c	Amiodarone f	Diltiazem, Verapamil, Dronedarone, Quinidine, Ranolazine, Bosentan, Olmesartan, Valsartan, Digoxin d
Herbal/Natural Supplements b	St. John's Wort, Echinacea, Milk thistle (i.e. silymarin), Chinese herb sho-saikoto (or Xiao-Shai-Hu-Tang)	
HMG-CoA Reductase Inhibitors e		Rosuvastatin (≤10 mg/day)
Other	Modafinil b , Sulfasalazine c , Methotrexate c	

- a Proton pump inhibitor (PPI) doses comparable with omeprazole 20 mg can be administered with SOF/VEL when SOF/VEL is administered with food. H2-receptor antagonists must not exceed a dose of 40 mg famotidine or equivalent and can be taken simultaneously with SOF/VEL and/or staggered by 12 hours. Antacids that directly neutralize stomach acid (i.e. Tums, Maalox) may not be taken within 4 hours (before or after) of SOF/GS-5816 administration.
- b May result in a decrease in the concentration of study drugs.
- c May result in an increase in the concentration of study drugs and/or concomitant medications
- d Monitor for signs and symptoms of digoxin toxicity.
- e Use with SOF/VEL may result in an increase in the concentration of HMG-CoA reductase inhibitor rosuvastatin.. Monitor for signs and symptoms of muscle weakness or myopathy, including rhabdomyolysis.
- f May result in symptomatic bradycardia. Mechanism is not currently known. The use of amiodarone is prohibited from **60 days prior to Baseline/Day 1** through the end of treatment

Medications for disease conditions **excluded** from the protocol (e.g., HIV-1 infection, active cancer) are not listed under this Concomitant Medication section and are disallowed in the study.

Subjects may not take any approved HCV medications during their participation in the study period.

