### 6.1. Screening Assessments

#### 6.1.1. Screening Visit (Day 28 to Day 0)

Subjects will be screened within 28 days of Baseline/Day 1 visit. The screening window can be extended to 42 days for subjects requiring liver biopsy, additional HCV genotype testing or for extenuating circumstances.

The following will be performed and documented:

- Obtain written informed consent

PPD

- Determine inclusion and exclusion eligibility
- Obtain medical history, including
  - Hepatitis C history
  - Liver transplant history
  - Liver biopsy results (if applicable)

- Determine cirrhosis status as defined in Section 4.1
  - If the presence of cirrhosis is determined, then appropriate diagnostic imaging (CT or Ultrasound) should be performed or confirmed to have been performed within 6 months of screening to exclude the presence of hepatocellular carcinoma (HCC)
- Determine treatment experience status as defined in Section 4.1
  - If treatment experienced, record the duration(s) and type(s) of the prior treatment administered.
  - If treatment experienced, record whether or not any past treatment regimens contained SOF or other nucleotide analogue HCV NS5B inhibitors.
- Complete physical examination including, vital signs (temperature, blood pressure, pulse, respiratory rate), body weight, and height
- Obtain details of concomitant medications
- Perform 12-lead ECG
- Fibrosis Assessment
- Calculate CPT score
- Obtain blood samples for tests as listed in Section 6.6.2:
  - Hematology
  - Chemistry
  - Coagulation tests
  - HCV RNA
  - Determination of HCV viral genotype and subtype
  - HCV antibody, HIV, and HBV surface antigen (HBV serology)
  - HbA1c
  - IL28B
  - Serum  $\beta$ -hCG pregnancy test for females of childbearing potential only

- Obtain urine sample for:
  - Urinalysis
  - Serum pregnancy test for females of childbearing potential
  - Urine drug screen
- Record any serious adverse events and all adverse events related to protocol mandated procedures occurring after signing of the consent form.
- Retests of Screening labs are permitted only if there is reason to believe the retest value will be within accepted parameters, for example, if the initial exclusionary value was either due to a sample processing error or due to an extenuating circumstance such as intercurrent illness.

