- Subjects meeting all of the inclusion criteria and none of the exclusion criteria will return to the clinic for the Baseline/Day 1 Visit assessments and enrollment into the study.

From the time of obtaining informed consent through the first administration of investigational medicinal product, record all serious adverse events (SAEs), as well as any adverse events related to protocol-mandated procedures on the adverse events case report form (eCRF). All other untoward medical occurrences observed during the screening period, including exacerbation or changes in medical history are to be captured on the medical history eCRF. See Section 7 Adverse Events and Toxicity Management for additional details.

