## **6.2. Treatment Assessments**

### **6.2.1. Baseline/Day 1 Visit**

The following baseline tests and procedures must be completed prior to enrollment and dosing/dispensing of study drug:

- Confirm eligibility (Reference Sections 4.2 & 4.3)
- Perform complete physical examination, including body weight
- Obtain vital signs (resting blood pressure, pulse, respiratory rate and temperature)
- Assessment of AEs and concomitant medications
- Conduct pregnancy prevention counseling
- Obtain blood samples for:
  - Hematology

- Chemistry
- Coagulation tests
- HCV RNA
- Viral sequencing
- Obtain blood sample for Pharmacogenomics testing (for subjects who have consented)

PPD

- Obtain urine samples for the following procedures:
  - Urinalysis
  - Pregnancy test for females of child bearing potential only
- Study Drug Administration
  - Dispense study drug as directed by the IWRS
  - Instruct the subject on the packaging, storage and administration of the study drug
  - Observe the subject taking the first dose of study drug and record the time of first dose and whether it was taken with or without food.

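### Exclusion 15 applies a 28-day interval to every prohibited drug and omits the 60-day amiodarone rule in the section it cites

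*Protocol*

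**What the plan says.** Exclusion 15 (Protocol Section 4.3) ends by excluding "or use of any prohibited medications listed in Section 5.4 within 28 days of the Baseline/Day 1 visit". It makes no exception for any drug.

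Section 5.4 sets 28 days for the interacting agents as a group, and its next sentence gives amiodarone its own interval: "The use of amiodarone is prohibited from 60 days prior to Baseline/Day 1 through the end of study drug dosing". Table 5-1 lists amiodarone as disallowed. Footnote f repeats the 60 days in bold and gives the reason: "May result in symptomatic bradycardia. Mechanism is not currently known".

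Entry is governed by the criteria lists. Section 6.1.1 says "Subjects meeting all of the inclusion criteria and none of the exclusion criteria will return to the clinic" for Baseline and enrollment. The first item under Section 6.2.1 is "Confirm eligibility (Reference Sections 4.2 & 4.3"; it does not cite Section 5.4. The same visit also includes "Assessment of AEs and concomitant medications".

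Section 5.4 also sets what must be recorded: "Concomitant medications taken within 30 days of Screening", continuing to the visit four weeks after study drug stops. On timing, Section 6.1.1 says "Subjects will be screened within 28 days of Baseline/Day 1 visit", extendable to 42 days for biopsy, further genotype testing or extenuating circumstances.

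**The concern.** The eligibility criterion is weaker than the safety rule it points to. Exclusion 15 carries its own number, so it can be read as taking only the list of drugs from Section 5.4 and fixing the interval at 28 days. On that reading a site can work correctly through Sections 4.2 and 4.3, find no criterion failed, and dose a subject whose amiodarone use Section 5.4 prohibits.

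The stake is the safety of individual subjects. The protocol names symptomatic bradycardia of unknown mechanism as the hazard and gives this one drug a longer interval than the rest. Later monitoring is not a substitute for the entry check. Appendix 2 schedules the 12-lead ECG at Screening only, the first scheduled vital signs after Day 1 are at Week 2, and none of the stopping rules in Section 3.4 names bradycardia.

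**Working it through.** The documents state no figure to reproduce here. The check compares the intervals and then asks how far back the required recording reaches.

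**1. The intervals, in days before Day 1**

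| Source | Interval for amiodarone |
|---|---|
| Section 4.3, exclusion 15 | 28 (general rule, no exception) |
| Section 5.4, sentence on amiodarone | 60 |
| Table 5-1, footnote f | 60 |
| Any other criterion in Sections 4.2 or 4.3 | none stated |

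The uncovered interval runs from day 29 to day 60: 60 − 28 = 32 days.

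**2. Whether a mismatch of this kind is harmless**

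Section 5.4 prohibits investigational agents from 28 days before Day 1, while exclusion 19 requires 3 months. There the eligibility list is the stricter of the two, so a site that follows it satisfies both. For amiodarone the order is reversed, and following the eligibility list does not satisfy Section 5.4.

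**3. Whether the required recording would reveal the use**

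Let S be the number of days from Screening to Day 1. Recording starts 30 days before Screening, so:

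- reach before Day 1 = 30 + S
- days of the 60 left unrecorded = max(0, 60 − (30 + S))
- days of the disputed 29–60 interval covered = min(60, 30 + S) − 28

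The documents give the limits S = 28 (ordinary) and S = 42 (extended). The values 7 and 14 are assumptions chosen to show the range, and 30 is the break-even point.

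| S | Reach (30 + S) | Unrecorded days of the 60 | Disputed days covered, of 32 |
|---|---|---|---|
| 7 | 37 | 23 | 9 |
| 14 | 44 | 16 | 16 |
| 28 | 58 | 2 | 30 |
| 30 | 60 | 0 | 32 |
| 42 | 72 | 0 | 32 |

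Full coverage needs 30 + S ≥ 60, that is S ≥ 30. In the ordinary window S ≤ 28, so the reach is at most 58 days. Only an extended screening period of 30 to 42 days covers the whole interval.

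**4. Other screens**

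- The medication history in Section 6.6.2 is taken on all subjects but states no look-back period, so it may or may not cover the rest.
- Exclusion 10 (screening ECG) and exclusion 17 (cardiac disease, in the investigator's opinion) are partial screens. Neither asks about the drug.
- The SAP plans a listing of treated subjects who did not meet eligibility criteria (listing 16.2.2.2). It would not be expected to show such a subject, because no criterion was failed. The deviation summary in SAP Section 4.3 might, but only after dosing.

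**The case against.** The strongest reply is that the 60-day rule is in the protocol's operative text. A site cannot apply the last clause of exclusion 15 without opening Section 5.4, where the amiodarone sentence follows directly on the 28-day sentence and the footnote repeats it in bold. Section 5.4 applies in its own right, so dosing such a subject breaches the protocol whatever exclusion 15 says, and a site that uses 60 days satisfies both rules. All of that stands, and it makes harm less likely. It does not remove the mismatch, because the criterion attaches a shorter interval of its own and the Day 1 eligibility check refers only to Sections 4.2 and 4.3.

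A second reply is that the recording rule sets what must be written down, not what a site may ask, and that the history in Section 6.6.2 has no limit. It adds that screening at 28 days leaves only 2 of the 60 days unrecorded, and that the larger gaps depend on assumed short screening intervals. These points are also fair. They show that a careful site will often learn of the use, but no text requires the question to be asked over 60 days.

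A third reply is that the ECG and vital-sign schedule would be the same with a corrected criterion. That is true: the schedule is no evidence that the missing clause causes harm. It matters only because little later monitoring is aimed at this risk, so the entry check carries most of the weight.

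**Conclusion.** The concern holds. Exclusion 15 states the wrong interval for amiodarone: 28 days against the 60 that Section 5.4 and Table 5-1 require, which leaves days 29 to 60 before Day 1 outside the eligibility criteria. The cross-reference and the medication reviews narrow the gap without reliably closing it, since the required recording reaches at most day 58 under ordinary screening.

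The conclusion rests on a literal reading of exclusion 15 and on 60 days being the sponsor's intended interval, which is stated twice. The documents give no rate of amiodarone use, so no subject count is estimated; the number is likely to be small. The point is minor but should be corrected, because it sits in an operative safety criterion. It has no bearing on the SVR12 analysis, its confidence interval or the sample size of 80.

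**What to change.** Add to exclusion 15: *or use of amiodarone within 60 days of the Baseline/Day 1 visit*. Have sites ask about amiodarone over the 60 days before Day 1 as part of the screening medication history in Section 6.6.2, and confirm the answer at the Day 1 concomitant medication review.

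The cost is one clause and one question within procedures already planned. No visits, tests or subjects are added. The clause alone aligns the text; the question makes sure the information needed to apply it is collected when screening is short.

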## **5. INVESTIGATIONAL MEDICINAL PRODUCTS**

### **5.1. Enrollment and Study Drug Supply**

This is an open-label study. An Interactive Web Response System (IWRS) will be employed to manage subject enrollment and the study drug dispensing as well as re-supply of study drug.

### **5.2. Description and Handling of SOF/VEL FDC**

#### **5.2.1. Formulation**

The SOF/VEL (400/100 mg) tablets are pink, diamond-shaped, film-coated tablets, debossed with “GSI” on one side and “7916” on the other side. In addition to the active ingredients, the SOF/VEL tablets contain copovidone, microcrystalline cellulose, croscarmellose sodium, magnesium stearate, polyvinyl alcohol, titanium dioxide, polyethylene glycol, talc, and iron oxide red.

#### **5.2.2. Packaging and Labeling**

SOF/VEL (400/100 mg) tablets are packaged in white, high density polyethylene (HDPE) bottles. Each bottle contains 28 tablets and polyester packing material. Each bottle is enclosed with a white, continuous thread, child-resistant screw cap with an induction-sealed, aluminum-faced liner.

SOF/VEL bottles to be distributed to centers in participating countries shall be labeled to meet all applicable requirements of the US Food and Drug Administration (FDA), EU Guideline to Good Manufacturing Practices – Annex 13 (Investigational Medicinal Products), and/or other local regulations.

#### **5.2.3. Storage and Handling**

SOF/VEL tablets should be stored at controlled room temperature until required for administration. Controlled room temperature is defined as 25°C (77 °F); excursions are permitted between 15°C and 30°C (59°F to 86°F).

All drug products should be stored in a securely locked area, accessible only to authorized site personnel. To ensure the stability of the study drug and to ensure proper product identification, the drug product should not be stored in a container other than the container in which they are supplied. Consideration should be given to handling, preparation, and disposal through measures that minimize drug contact with the body. Appropriate precautions should be followed to avoid direct eye contact or exposure through inhalation when handling SOF/VEL tablets.

Sufficient quantities of SOF/VEL tablets to complete the entire study will be shipped to the investigator or qualified designee from Gilead Supply Management Team (or its designee).

### **5.3. Dosage and Administration**

SOF/VEL tablet is to be administered once daily with or without food. Each subject must be given instructions to maintain approximately the same daily dosing interval between study drug doses.

For a missed dose of study medication, subjects must be instructed to take the missed dose of study medication as soon as possible during the same day. Subjects should be cautioned never to double the next dose with a missed dose of study drug under any circumstances.

### **5.4. Prior and Concomitant Medications**

Concomitant medications taken within 30 days of Screening, up to and including the date of the visit four weeks after discontinuation of study drug, need to be recorded in the source documents and eCRFs. All concomitant medications should be recorded in the source documents (including all blood products).

For subjects on a calcineurin inhibitor (e.g., tacrolimus, sirolimus, everolimus) for post-transplant immunosuppression, levels should be collected as per the standard schedule (or as clinically indicated) for dose management at the clinical site, and processed at the local laboratory. Management of the immunosuppression is not part of the clinical protocol, but levels and resulting dose adjustments will be recorded to assess whether the regimens required adjustment in correlation with resolution of the HCV infection.

The following medications are prohibited from 28 days prior to the Baseline/Day 1 visit through the end of study drug dosing:

- Use of corticosteroids at any dose > 5mg of prednisone/day (or equivalent dose of corticosteroid) for maintenance of immunosuppression is prohibited. However, use of steroids for the short term treatment of Acute Cellular Rejection (ACR) is up to the discretion of the Investigator.
- Investigational agents or devices for any indication

Concomitant use of certain medications or herbal/natural supplements (inducers of drug transporters i.e. P-gp) with study drug may result in pharmacokinetic interactions resulting in increases or decreases in exposure of study drug or these medication. The use of the following agents is prohibited from 28 days prior to Baseline/Day 1 through the end of study drug dosing. The use of amiodarone is prohibited from 60 days prior to Baseline/Day 1 through the end of study drug dosing.

Examples of representative medications which are prohibited or are to be used with caution are listed below:

